2	06.04.20	Editing of content and structure prescreening help pages in the light of expert advice Increased funding to pay participants up to £60 for taking part. This reward was originally going to be paid in Amazon Vouchers, but we have found out that payment with Love to Shop shopping vouchers will be easier to administrate. Feedback from our youth advisors indicated that certain minor wording changes and re- ordering of some information might better explain our procedures. We have advised participants in the information sheet that they need Wi-Fi or data to use the App. Addition of 2 questions relating to the impact of COVID-19 on ppts.	
3		Our collaborator Monsenso informed us that they would be collecting personal information in the form of name and gender for their system to work. The data protection officer for the University of Exeter also changed. This necessitated small changes in the wording of our data protection and privacy policy.	03.06.20
4	03.08.2020	The data protection form has been edited with tracked changes to remove reference to Qualtrics (our survey website provider) collecting participant IP addresses. This is because we have been able to work with Qualtrics to avoid the unnecessary collection of IP addresses. This necessitated the editing of a new data protection policy	
		Our trial recruitment website (mymoodcoach.com) has now been created and connected to the Qualtrics survey system. Our recruitment website provides potential participants with the information sheet and study information including promotional videos and infographics before they take part so they are fully informed. The ethics committee were asked to review the website.	
5	10.09.2020	The trial end date is now being extended because of delays starting recruitment. The new trial end date is expected to be September 2022 so this has necessitated changes in the	17/09/2020

		information sheet, consent form and data protection and privacy policy.	
		We have found out from our App developer that the App will only work on Android software version 8 or more so need to update our information sheet with this information.	
6	25.03.21	These amendments relate to work package 8 (WP8).	13/04/2021
		As outlined in the original application (Task 8.1/8.2), in-depth, semi-structured interviews will be conducted with a self-selected sample of up to 50 young people participating in the trial across sites at 3-month follow up (from February 2021 onwards). The purpose of conducting the qualitative interviews is to broadly determine the barriers and facilitators to successful implementation of MyMoodCoach. A summary of the study protocol for WP8 is available in Appendix A.	
		Changes have been made to the WP8 Consent Form and Information Sheet C (V0.8) for the 3-month follow-up interviews to reflect the revised WP8 protocol.	
		The study protocol (Appendix A) also outlines details of an embedded sub-study (Task 8.3) with vulnerable or underserved groups. In addition to semi-structured interviews with trial participants at 3-month follow-up, semi- structured interviews will be also conducted with a sample of up to 30 young people from vulnerable or underserved groups, who are typically unrepresented in research or who are less likely to access services and interventions, not currently participating in the trial. The purpose of this study is to explore acceptability rather than efficacy of the intervention.	
		A new Consent Form and Information Sheet D (V0.3) has been drawn up for the embedded sub-study.	
		An updated Privacy Notice and Data protection Policy has been drawn up for WP8 for both the primary interview study (Form C V.01) and the embedded sub-study (Form D V.01)	

		Finally, a risk management plan has been adapted from the original SOP for WP8 (WP8 Risk Management Plan V0.2 25.03.21).	
7	27.05.21	This amendment refers to work package 8 materials only. A section of text referring to the voice analysis was missed from their information sheet and data protection form so this has been corrected and new versions approved.	28.05.21
8	05.07.21	At the point that our original recruitment target of 2142 was recruited. Due to technical problems with the Monsenso app and its supporting server hosted by OVH, all participants were affected by the app being unavailable for approximately 1 month, badge (reward data) was out of date for many accounts for 2 months, and many Monsenso accounts were lost (some ppts started again on new accounts but some chose not to). As this was just after a major recruitment drive at all sites it is estimated that some 1500 participants were affected to varying degrees and this number had to be recruited again. Those that had already completed 1 and 3 month (primary outcome measure time point) follow ups were considered to have not been affected). Those recruited after the disruption were also considered not to have been affected. This amendment describes how that increase in sample size was calculated (increased from 2142 to 3600 plus) and how the analysis will be adapted to address the expected impact on our outcome data. Outcome data collection was collected on a separate system and therefore not directly affected by the data loss.	

Assessing and Enhancing Emotional Competence for Well-Being (ECoWeB) in Young Adults: A principled, evidence-based, mobile-health approach to prevent mental disorders and promote mental well-being

ECoWeb: The Emotional Competence for Well-Being in Young Adults Study

RESEARCH REFERENCE NUMBERS

University of Exeter CLES Ethics Committee reference: eCLESPsy000048 v3.0

ClinicalTrials.gov Identifier: NCT04148508

SIGNATURE PAGE

The undersigned confirm that the following protocol has been agreed and accepted and that the Chief Investigator agrees to conduct the trial in compliance with the approved protocol and will adhere to the principles outlined including clinical trial regulations, GCP guidelines, the Sponsor's SOPs, and other regulatory requirements.

I agree to ensure that the confidential information contained in this document will not be used for any other purpose other than the evaluation or conduct of the clinical investigation without the prior written consent of the Sponsor.

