	work experience as well as academic study and to be focused on last 3 months, and added a separate question about changes or transitions in life.	
Occupational status	The participant is asked to provide information on current occupation, which is then used to classify the participant into an occupational class, using standardized international class schemes based on the EGP (Erikson, Goldthorpe and Portocarero) scheme and using a standard approximation to this scheme, the International Socio-Economic Index of Occupational Status (ISEI) developed by Ganzeboom et al. (1992, 1996). Because this is a young sample aged 16-22 and a number will not yet be in the workforce, we will also assess parental (mother and father) occupational status in order to estimate socio-economic status for each individual.	This socio-economic status scale has a range from 10 to 90. At the bottom are unskilled manual jobs in which wages and levels of education are low and at the top are the professionals, proprietors, and managers. A distinction is made between upper and lower non-manual classes, skilled and unskilled manual classes, farmers and other self- employed. This is a well-established and frequently used means to classify occupations and estimate socio-economic status, that has high reliability and validity and is recommended by the guidelines report on monitoring socio-economic inequalities in health in the European Union, prepared by the Health Monitoring Program of the European Commission. It allows us to assess occupational status mobility by examining whether occupational status has increased, decreased or stayed the same over the assessment time points.
COVID-19 (supplementary question)	Since the COVID-19 pandemic began UK charities and mental health organisations have been reporting poorer mental health in young people. This may change over the course of the trial and possibly between recruitment and follow up when restrictions are lifted. The following questions aim to capture whether at the time of assessment lockdowns are in place, and the impact of those lockdowns on ppt mental health.	New measures: Are your current movements restricted by any lock down due to Coronavirus Not at all (1)(7) completely restricted To what extent is the coronavirus pandemic affecting your mental health now? Not at all (1)(7) very much affected

Health Economics Measures

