10.2 Planned recruitment rate

Recruitment will take place over up to 52 weeks across 4 sites. It is estimated that an average of 14 potential participants (eligible for one of the trials and consenting to participate) will be recruited per site per week, leading to expected recruitment of 2912 potential participants (assuming recruitment across all weeks). This exceeds the required sample size for the overall recruitment cohort (2142 potential participants). The planned recruitment rate was dramatically increased for the last 2 months of recruitment to cope with the change in sample size.

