### 6.9 Addressing protocol violations due to app outage

Due to a fire at the Monsenso site on 10/03/2021, the app was unavailable between 10/03/2021 and 25/03/2021. Therefore, participants who registered for the trial and were randomised to receiving a version of the app did not have the app available for a period of time. It is the intention that the app intervention is available to participants for the full 12-month period of follow-up. However, it is anticipated that the majority of therapeutic effect will take place during the first 4 weeks of the intervention period.

Based on a total of 2141 participants who had registered prior to the app outage:

- Those participants due both 1m and 3m FU (i.e., either completed or past the timepoint to complete) before 10 March (i.e., only 12m FU potentially impacted by lack of app availability), N = 446
- 2. Post 1m but prior to 3m FU before 10 March (i.e., potential impact of app outage on 3m and 12m FU). Those who had not reached the date their 3-month follow-up was due by 9th March but had passed the date on which their 1 month follow up was due (1 month follow up was due on or before 9th February 2021) N= 465
- 3. Those signed up to study but not completed 1m FU before 10 March (this will roughly correspond with those who signed up between 12 Feb and 10 March the participants most severely affected by the app outage potentially impact of outage on 1m, 3m and 12m FU), N = 992. This group can be further divided:
  - Never logged on: N= 319 (all have been re-invited twice) on average before the app outage, 20% of participants never signed into the app
  - Has old MSS account, N= 83 (old account not lost, badge data will be re-added)
  - Had old MSS account and account lost-AND have not set up themselves up on a new account, N= 389
  - Data lost, new account set up and ppt starting again (what badge data we have will be added back) N=201
- 4. Signed up after 25 March unaffected by app outage as there was a new server up and running when they signed up. N=238. These ppts are affected by the intermittent app stability issues, but not the fire or badge data not showing correctly

Several analytical approaches to address this issue are available.

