#### 3-month analyses (observed outcome data only)

The primary analysis using the intention to treat principle (all recruited participants will be analysed according to their randomised group) will be carried out using all observed data, combining data from the original sample with data from the additional participants recruited to replenish the sample following the disruption due to app outage.

For comparison with the primary analysis, two further post hoc sensitivity analyses are proposed.

- 1. Exclusion of participants whose intervention was disrupted prior to 3-month follow-up (Groups 2 and 3).
- 2. Primary analysis with addition of a covariate to indicate postulated level of disruption due to app outage (0 for Groups 1 and 4 (little/no disruption); 1 for Group 2 (moderate disruption); 2 for Group 3 (severe disruption)). Although this is a post-randomisation covariate, it is thought to be distributed randomly across treatment groups (i.e. all treatment groups were affected equally by the app outage). As an extension to this model, an interaction term, to model the interaction between treatment group and level of disruption, will be added to this model, with the aim of exploring whether there is any evidence to indicate any variation in the effect of disruption across the three treatment groups.

Comparison of these analyses will allow estimation of the between treatment group differences at specified levels of disruption (i.e. due to disruption occurring at different times during treatment delivery and follow-up). All of the above are post hoc exploratory analyses only, performed in response to the unforeseen app outage. Analysis 2 in particular, should be viewed with caution as it includes a post-randomisation covariate. However, disruption due to app outage is distributed evenly across treatment groups, and it is reasonable to assume that distribution is also effectively random (i.e. timing of recruitment is thought to be random; there is no difference between participants recruited at such a time as to be affected by the app outage and those that were not).

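### SAP 6.9 treats recruitment timing as random, but disruption level is set by enrolment date, so differences between disruption levels cannot be attributed to the app outage

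*Protocol*

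**What the plan says.** SAP section 6.9 sorts participants by where they stood when the app went down on 10 March 2021. Group 1 (446) was past the 3-month follow-up, Group 2 (465) was between 1 and 3 months, and Group 3 (992) had not reached 1 month. Group 4 (238) signed up after 25 March, on a new server. Of Group 3 the SAP says "this will roughly correspond with those who signed up between 12 Feb and 10 March". A further 1457 participants are to be recruited to replace Groups 2 and 3.

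The 3-month primary analysis is intention-to-treat on all observed data. Two analyses are set beside it. One drops Groups 2 and 3. The other adds a covariate coded 0 for Groups 1 and 4, 1 for Group 2 and 2 for Group 3, and is then extended by its interaction with arm. The SAP calls both post hoc and exploratory. It urges caution over the covariate model because the covariate arises after randomisation, and then answers that caution: "disruption due to app outage is distributed evenly across treatment groups, and it is reasonable to assume that distribution is also effectively random". The stated ground, which sets the affected beside everyone else, is that "timing of recruitment is thought to be random; there is no difference between participants recruited at such a time as to be affected".

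The protocol describes enrolment differently. Amendment 8 says of the outage: "As this was just after a major recruitment drive at all sites it is estimated that some 1500 participants were affected to varying degrees". Section 10.2, on the period after the sample size was raised, says: "The planned recruitment rate was dramatically increased for the last 2 months of recruitment". The COVID-19 entry in section 3.3, having noted reports of a decline in wellbeing among the young, adds: "This may change over the course of the trial and possibly between recruitment and follow up when restrictions are lifted".

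**The concern.** The SAP's argument runs two claims together. That disruption is balanced across arms follows from randomisation and is sound. That the disruption groups are comparable with each other is a separate claim, and randomisation does not supply it. A participant's level depends only on the date of enrolment, and the dates are not interchangeable: they differ in recruitment drive, phase of the pandemic and app server.

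The planned models do little to separate these. They carry the primary-analysis covariates of SAP 6.3 (baseline score, age, country, and anything unbalanced across arms) and have no term for period or recruitment wave. Lockdown status enters only in the separate sensitivity analyses of SAP 6.7. Code 0 pools people enrolled well before the outage with people enrolled after it. Table A.1 shows disruption by arm, but no table shows baseline characteristics by disruption group.

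The stake is interpretation. The SAP wants these comparisons to yield arm differences at each level of disruption. It also says the 3-month results will inform whether outage analyses are run at 12 months and for the repeated measures. A smaller effect in Groups 2 and 3 could be put down to lost app access when something else tied to the calendar produced it.

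**Working it through.** **1. The plan's own counts reproduce.** From SAP 6.9: 446 + 465 + 992 + 238 = 2141; the four subgroups of Group 3, 319 + 83 + 389 + 201 = 992; Groups 2 and 3, 465 + 992 = 1457; revised target, 2142 + 1457 = 3599.

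**2. Disruption level against enrolment date.** All 1457 in Groups 2 and 3 enrolled by 10 March 2021. The SAP gives replenishment recruits no code; the natural reading is 0. The undisrupted then number 446 + 238 + 1457 = 2141, of whom 238 + 1457 = 1695 enrol after 25 March: 1695/2141 = 79%. With the SAP's minimum replenishment of 992, the share is (238 + 992)/(446 + 238 + 992) = 1230/1676 = 73%. At 12 months, the option that excludes Groups 1 to 3 leaves only people enrolled after 25 March, so that comparison is wholly a split by period.

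**3. Size of the surge.** The planned rate is 14 × 4 = 56 per week (SAP 5.3). The observed rate depends on dates in SAP 6.9 that do not agree.

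- If Group 3 signed up from 12 February to 10 March (26 days): 992/26 × 7 = 267 per week, or 267/56 = 4.8 times plan. Group 2 then runs from about 9 December to 9 February (62 days): 465/62 × 7 = 52.5 per week. Ratio 267/52.5 = 5.1.
- If Group 2's bracket governs (1-month follow-up due by 9 February, so enrolled by about 9 January, 31 days): 465/31 × 7 = 105 per week. For the groups to cover everyone, Group 3 must start about 9 January (60 days): 992/60 × 7 = 116 per week. Ratio 116/105 = 1.1, and 116/56 = 2.1 times plan.

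**4. What could follow.** The 3-month models were simulated for PROMOTE with no outage effect at all. Settings: SD 11.3, true effect of the personalised app over usual practice 3.0, 70% of the cohort in PROMOTE, 60% observed, 1:1:1, 600 runs per scenario, disruption as a linear score, no baseline adjustment. The differences given to Group 3 are assumptions.

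| Assumed for Group 3 | Effect, all | Effect, Groups 2 and 3 excluded | Disruption coefficient per level (share significant) | Arm-by-disruption interaction per level (share significant) |
|---|---|---|---|---|
| No difference | 3.02 | 2.98 | -0.01 (6.5%) | 0.04 (6%) |
| Scores 1 point lower | 2.95 | 2.93 | -0.48 (31%) | 0.01 (3%) |
| Scores 2 points lower | 3.04 | 3.05 | -0.95 (82%) | 0.00 (4%) |
| Scores 3 points lower | 3.01 | 3.02 | -1.42 (98%) | -0.01 (3%) |
| Responds 1.5 points less | 2.62 | 3.02 | -0.26 (12%) | -0.69 (14%) |
| Responds 3 points less | 2.20 | 3.05 | -0.45 (28%) | -1.44 (42%) |

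A difference in level moves the disruption coefficient and leaves the arm contrast alone. A difference in response also opens a gap between the all-participant and undisrupted estimates, although no outage effect was simulated.

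**5. Precision if code 0 is split.** Group 1 in PROMOTE: 446 × 0.7/3 × 0.6 = 62 analysed per arm; SE of an arm contrast 11.3 × √(2/62) = 2.0 points. Post-outage: 1695 × 0.7/3 × 0.6 = 237 per arm; SE 11.3 × √(2/237) = 1.04. SE of the difference between the two: √(2.03² + 1.04²) = 2.3. Group 1 in PREVENT: 446 × 0.3/3 × 0.6 = 27 per arm.

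**The case against.** The SAP hedges its statement, labels the outage analyses post hoc and exploratory, and keeps intention-to-treat on all participants as primary. That stands, and it limits how serious the point is. But the caution it gives concerns a covariate that arises after randomisation, and the disputed statement is then used to ease that caution.

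A reader might infer that the recruitment drive brought in different people, so that the outage analyses would misattribute their effects. The documents do not show that. They show uneven timing. All sites used the same website, screening and eligibility rules, and no baseline difference is reported. The simulated shifts are assumptions. What remains is that the SAP's statement of no difference is just as unsupported, and that period and platform can matter even if the intake was identical.

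A reader might also infer that the trial's treatment effect is biased. It is not: enrolment date does not depend on arm, so arm contrasts stay randomised overall and within each level.

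Baseline score, age and country are in the outage models and should absorb part of any difference in who enrolled. They do not address when people enrolled or which server they used.

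Finally, the size of the surge is insecure. Group 3 enrolled about 5 times or about 1.1 times as fast as Group 2, depending on which date governs. An intermediate figure of 2.5 (267/105) mixes the two readings and leaves 9 January to 12 February with no enrolment, so it should not be used.

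**Conclusion.** The point holds in a limited form. The statement that timing is random and that affected and unaffected participants do not differ has no support in the documents and sits badly with the recruitment drive, the later acceleration and the change of server. Disruption level is close to a marker of enrolment period: every disrupted participant enrolled by 10 March 2021, and 79% of undisrupted participants on target numbers (73% at minimum replenishment) enrol after 25 March. The disruption coefficient, the arm-by-disruption interaction and the all-versus-undisrupted gap are therefore non-randomised contrasts. They could reflect lost access, recruitment wave, calendar period, lockdown or platform, and the planned models cannot say which. The amount of confounding is unknown and may be nil. The conclusion does not depend on how large the surge was. It rests on the group definitions in SAP 6.9 and on replenishment recruits being coded 0.

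**What to change.** In SAP section 6.9:

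1. Delete the statement that recruitment timing is random and that the groups do not differ. Describe contrasts between disruption levels as non-randomised, not as the effect of the outage.
2. Enter disruption as a categorical factor, with code 0 split into pre-outage (Group 1) and post-outage (Group 4 plus replenishment). Report the arm effect with its 95% confidence interval in each level.
3. Tabulate baseline characteristics, country and lockdown rating by disruption group.
4. Add the baseline lockdown rating, already collected, as a covariate in the outage models.
5. Reconcile the Group 2 and Group 3 dates. Also correct the description of the 2141 as registered before the outage, since it includes the 238 who signed up after 25 March.

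Two additions are best avoided. A rule that attributes an effect to disruption once it exceeds the Group 1 versus post-outage gap would be mostly noise (SE about 2.3 points against a 3.0-point target difference), and it would say nothing about Group 3's intake. Stacking further arm interactions would add terms with little power.

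The cost is SAP wording, one extra factor level, one table and one covariate, with no new data. The drawback is that Group 1 is small: about 62 analysed per arm in PROMOTE (SE about 2.0 points) and about 27 per arm in PREVENT. Its estimate will be imprecise and only descriptive.

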ISF	Investigator Site File (This forms part of the TMF)
ISRCTN	International Standard Randomised Controlled Trials Number

Marketing Authorisation
Member State
Principal Investigator
Participant Identification Centre
Participant Information Sheet
Project Management Team
Quality Assurance
Quality Control
Qualified Person
Randomised Control Trial
Research Ethics Committee
Serious Adverse Event
Statistical Analysis Plan
Serious Adverse Reaction
Source Data Verification
Standard Operating Procedure
Site Specific Information
Suspected Unexpected Serious Adverse Reaction
Trial Master File
Trial Management Group
Trial Protocol
Trial Steering Committee
Work Package (Lead)
Youth Advisory Board

Location/Collaborator Abbreviations

EXCTU	Exeter University Clinical Trials Unit
UNEXE	The University Of Exeter
LMU	Ludwig-Maximilians Uplattplniversitaet Muenchen
UGENT	Universiteit Gent
AUD	Audeering GMBH
UJI	Universitat Jaume I De Castellon
ICCS	Institute Of Communication And Computer Systems
MSS	Monsenso Aps
UOXF	The University Of Oxford
BUT	Vysoke Uceni Technicke V Brne
FRAU	Fraunhofer Gesellschaft Zur Foerderung Der Angewandten Forschung E.V.
UNIGE	Universite De Geneve
UCPH	Kobenhavns Universitet
DJI	Deutsches Jugendinstitut Ev

iii ECoWEB Project Summary

The European Commission funded ECoWeB project consists of consortium of academic researchers and technical collaborators who are conducting two major tasks:

- A new self-help app will be designed to improve wellbeing and prevent mental ill health in young adults
- This new app will be tested in the cohort randomised controlled ECoWeB study. Two randomised controlled trials called ECoWeB PROMOTE and ECoWeB PREVENT will be run from the ECoWeB study cohort.

Multiple academic partners (LMU, UGENT, UNEXE, UNIGE, ICCS) have worked together to create the content of the self-help app and technical collaborators MSS and AUD are hosting the app, and conducting audio analysis respectively. 4 academic sites will recruit for the trial (UNEXE, UJI, UGENT, LMU) and EXCTU will collect and store data on behalf of the UNEXE.

Although there are effective mental well-being promotion and mental illness prevention interventions for young adults, there is a need for more robust evidence on resilience factors, for more effective interventions, and for approaches that can be scalable and accessible at a population level. To tackle these challenges and move beyond the state-of-the-art, the ECoWeB project uniquely integrates three multidisciplinary approaches:

(a) For the first time to our knowledge, we will systematically use an established theoretical model of normal emotional functioning (Emotional Competence Process) to guide the identification and targeting of mechanisms robustly implicated in well-being and general distress and psychopathology in young adults

(b) A personalised medicine approach: systematic assessment of personal Emotional Competence (EC) profiles is used to select targeted interventions to promote well-being

(c) Mobile application delivery to target scalability, accessibility and acceptability in young adults.

Our aim is to **improve mental health promotion** by developing, evaluating, and disseminating a comprehensive mobile self-help app to assess deficits in three major components of EC (production, regulation, knowledge) and to selectively augment pertinent EC abilities in adolescents and young adults. It is hypothesized that the targeted interventions, based on state-of-the-art assessment, will efficiently increase resilience toward adversity, promote mental well-being, and potentially act as primary prevention for mental ill-health. The EC intervention will be tested in cohort multiple randomized trials with young adults from many

European countries against a usual care control and an established, non-personalised socioemotional learning digital self-help intervention. Building directly from a fundamental understanding of emotion in combination with a personalised approach and leading-edge digital technology is a novel and innovative approach, with potential to deliver a breakthrough in effective promotion of well-being and prevention of poor mental health.

Table 6 Summary of Study

Trial Title	Assessing and Enhancing Emotional Competence for Well-Being (ECoWeB) in the Young: A principled, evidence-based, mobile-health approach to prevent mental disorders and promote mental well-being	
Internal ref. no. (or short title)	ECoWeb: Emotional Competence for Well-Being	
Clinical Phase	111	
Trial Design	Phase III superiority parallel 3-arm randomised multicentre, multinational cohort randomized controlled trials (cmRCT)	
Trial Participants	European young adults (aged 16-22 years) in a population-oriented public health approach	
Planned Sample Size	2400 for overall cohort, (adjusted to 3600 plus after the technical difficulties).	
	Two trials are running within the one cohort.	
Treatment duration	Indefinite self-help app use by young people, anticipated main usage 1-2 months	
Follow up duration	Over 12 months (one month, three months, twelve months)	
	The primary time point is three months	
Planned Trial Period	24 months (starting recruitment to final follow up)	
	RCTs & measures	Outcome domains
Primary outcome	ECoWeB-PROMOTE (PROMOTION of well-being and good mental health) – Mental Wellbeing (WEMWBS)	Indices of well-being and poor mental health
	ECoWeB -PREVENT (PREVENTION of general distress, poor mental health and emotional disorders) - Depression (PHQ-9)	
Secondary outcomes	Anxiety GAD-7	Non-specific indices of poor mental health
	Functioning – WSAS	
	Functioning – WSAS Health-related quality of life – EQ5D-3L	
	Health-related quality of life –	

	Assembled from multiple indices: rumination, appraisals, emotional knowledge and perception	
Intervention	Three intervention groups:	
	1. Tailored Emotional Competence self-help delivered via app	
	2. Self-help cognitive-behavioural approach app	
	3. Usual practice and self-monitoring app (control).	
	The active interventions are all entirely self-help and provide psychoeducation, tips, advice and strategies for well-being promotion.	
Route of Administration	Phone App (IOS and Android)	

iv. FUNDING

Table 7 Funding and Support in Kind

FUNDER(S)	FINANCIAL	AND NON GIVEN
Horizon 2020	EUR 3 999 980	

Table 8 Funding arrangements for the ECoWeB project:

Country	Organisation	Amount
UK	UNIVERSITY OF EXETER	EUR 1 031 661,25
Germany	LUDWIG-MAXIMILIANS- UNIVERSITAET MUENCHEN	EUR 1 168 375
Belgium	UNIVERSITEIT GENT	EUR 561 681,25
Germany	AUDEERING GMBH	EUR 221 437,50
Spain	UNIVERSITAT JAUME I DE CASTELLON	EUR 307 312,50
Greece	INSTITUTE OF COMMUNICATION AND COMPUTER SYSTEMS	EUR 175 750
Denmark	MONSENSO APS	EUR 213 950
UK	UNIVERSITY OF [name], Oxford	EUR 227 431,25
Czeck Republic	VYSOKE UCENI TECHNICKE V BRNE	EUR 15 000
Germany	FRAUNHOFER GESELLSCHAFT ZUR FOERDERUNG DER ANGEWANDTEN FORSCHUNG	EUR 15 000
Switzerland	UNIVERSITE DE GENEVE	EUR 15 000
Denmark	OBENHAVNS UNIVERSITET	EUR 15 000

Germany DEUTSCHES JUGENDINSTITUT EV EUR 32 381,25	
---	--

v. ROLE OF TRIAL SPONSOR AND FUNDER

Role of Funder

The research funder has the responsibility to ensure that there is a proper use of the funds they control. The study is funded by the European Commission. The Funder has conducted a review of the study, provided feedback to the consortium, and has established that the research is worthwhile, of high scientific quality and represents good value for money. The research funder has assessed the experience and expertise of the Chief Investigator, other key researchers on the programme and has deemed that there is appropriate infrastructure for the research to be carried out.

The funder plays no further role in the design of this individual study and will have no role in data analysis or interpretation or writing up of findings of the study. The funder will be sent all outputs prior to dissemination but has no role in the decision to submit for publication.

Role of Sponsor

The study sponsor will ensure that the research team has access to resources and support to deliver the research as proposed and that responsibilities for management, monitoring and reporting of the research are in place prior to the study commencing. The sponsor will ensure that there is agreement on recording, reporting and reviewing significant developments as the research proceeds and approve any modifications to design, obtaining requisite regulatory authority.

The sponsor will assume responsibility for operating the management and monitoring systems of the research. Prior to the study commencing the sponsor will be satisfied that:

- The research will respect the dignity, rights, safety and well-being of participants and the relationship with healthcare professionals.
- The research will be reviewed and approved by the appropriate Research Ethics Committee.
- The Chief Investigator, and other key researchers have the requisite expertise and have access needed to conduct the research successfully.
- The arrangements and resources proposed for the research will allow the collection of high quality, accurate data and the systems and resources will allow appropriate data analysis and data protection.
- Organisations and individuals involved in the research agree the division of responsibilities between them.
